3. Currently using illegal drugs (e.g., cocaine, methamphetamine, opiates) (safety risk and potential confounding)
4. Current smoker who does not agree to stop (confounding)
5. Participation in routine (>1 x/week) exercise program (may improve glucose metabolism/vascular function)
6. History of heart disease, orthopedic, metabolic or neurological condition that would contraindicate exercise (safety risk)

Inclusion of Women and Minorities

Women and members of all races and ethnic groups are eligible for this trial. Men are not eligible.

7.c Subject Recruitment Plans and Consent Process

Participants will be recruited from the Center of Women's Health at Washington University School of Medicine/Barnes Jewish Hospital. All obese (BMI \geq 30) patients with on-going pregnancies will be approached for study participation at the first visit in the the trained clinical research coordinator. Patients will be approached through direct personal recruitment through the clinic and consented.

7.d Early Withdrawal of Subjects

Research participation will occur on three separate visits. Participants will be withdrawn if they are unable to complete the procedures during any of the research visits.

7.e Data Collection and Follow-up for Withdrawn Subjects

There will be no follow up of withdrawn participants.

D Study Procedures

D1 Screening for Eligibility

Pregnant women with obesity: Eligibility criteria of patients attending the Center of Women's Health at Washington University School of Medicine/Barnes Jewish Hospital will be reviewed by [name] and by the research coordinator.

D2 Visit 1

These procedures will be performed on over 3 visits separated by \geq 4 days. Participants will be studied within gestation weeks 23-30. The evening before the study visits, participants will consume a standardized meal consisting of 55% carbohydrate, 30% fat, and 15% protein provided by the WUSM Bio-Nutrition Facility. The following morning, fasted participants (10 hrs) will be admitted to the Clinical Translational Research Unit of the Institute of Clinical and Translational Sciences at Washington University School of Medicine (WUSM CTRU) at 8:00 am. Maternal weight (calibrated scale) and height (stadiometer) will be measured.

Body Composition Measurement: Whole-body fat will be quantified using through skin-fold anthropometry (Harpenden, West Sussex, UK).

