Assessment of Laboratory Clinical Variables: Venous blood will be collected from the participants to assess 1) CBC, 2) HbA1C, 3) complete metabolic panel, and blood hormone/metabolites including plasma glucose, insulin, c-peptide, free fatty acid, placental growth factor and vascular endothelial growth factor (VEGF).

The participant will quietly lie in bed for 45 minutes.

Immediately following the 45-minute rest period:

Assessment of Laboratory Clinical Variables: Venous blood will be collected from the participants to assess 1) CBC, 2) HbA1C, 3) complete metabolic panel, and blood hormone/metabolites including plasma glucose, insulin, c-peptide, free fatty acid, placental growth factor and vascular endothelial growth factor (VEGF).

Assessment of Vascular Function

Endothelial Function: Reactive hyperemia peripheral tonometry (RHPT, EndoPAT2000, Itamar Medical, Caesarea, Israel) will be measured before, and immediately post-exercise to assess digital pulse volume responses to arterial occlusion (blood pressure cuff). Briefly, the participant is placed in a sitting position and two disposable, inflatable probes are placed on the index fingers. Following 10 min of baseline signal recording, a blood pressure cuff is inflated for 3-min and following release, the hyperemic response is recorded for 5-min. The EndoPAT 2000 has good reproducibility (ICC=0.74) and has been validated as a measure of endothelial function with an 82% sensitivity and 77% specificity to diagnose coronary endothelial dysfunction⁵².

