Large Artery Function: Central aortic blood pressure and pressure waveforms. Pressure waves will be recorded sequentially from different sites, and transit time calculated using registration with a simultaneously recorded ECG by use of the SphygmoCor™ system (AtCor, Sydney, Australia), which has been well-validated and is approved by the FDA for the noninvasive assessment of central blood pressures and central aortic compliance by measurement of pulse wave velocity (PWV) and augmentation index (AIx). In this system, a single high-fidelity applanation tonometer (Millar) is used to obtain a proximal (i.e. carotid artery) and distal pulse (i.e. radial or femoral) recorded sequentially a short time apart; from this, the PWV is calculated from the transit time between the two arterial sites, determined in relation to the R-wave of the ECG. The time between the ECG and the proximal pulse is subtracted from the time between ECG and distal pulse to obtain the pulse transit time. In the case of stiff arteries, PWV rises and the reflected wave arrives back at the central arteries earlier, adding to the forward wave and augmenting the systolic pressure. This phenomenon can be quantified through the augmentation index (AIx), which is defined as the difference between the second and first systolic peaks (P2-P1) expressed as a percentage of the pulse pressure

Central hemodynamics and aortic compliance will be characterized using the SphygmoCor™ system. Pressure waves will be recorded sequentially from different sites using the SphygmoCor™ system (AtCor) using methods described by our group.⁵³ Derived indices include the central blood pressures and central aortic compliance characterized as the augmentation index (AIx) and pulse-wave velocity (PWV).

At 60-minutes following the end of the rest period:

Assessment of Glucose Metabolism

Two-hour oral glucose tolerance test (OGTT): At 60-min following the end of the rest period, a 2-hr oral OGTT will be conducted. Venous samples for glucose, insulin, and C-peptide will be drawn at time 0 and then 30, 60, 90 and 120 minutes after starting

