ingestion of glucola (1.75 g/kg of body weight to a maximum of 75 g). Insulin sensitivity and insulin secretion will be estimated by the Matsuda Whole-Body Composite Insulin Sensitivity Index (ISI), HOMA-IR, Insulinogenic Index and C-peptide Index. $ISI = 10\,000 / \sqrt{(\text{glucose}_{\text{fasting}} \times \text{insulin}_{\text{fasting}}) (\text{glucose}_{\text{mean}} \times \text{insulin}_{\text{mean}})}$, $HOMA-IR = (\text{Insulin}_{t0} \text{ mU/L} \times \text{Glucose}_{t0} \text{ mmol/L}) / 22.5$, Insulinogenic Index ($\Delta I_{30} / \Delta G_{30}$) and C-peptide index ($\Delta C\text{-peptide}_{30} / \Delta G_{30}$) will be calculated as previously described⁵⁴⁻⁵⁶. Area under the curve for glucose, C-peptide and insulin levels will also be calculated by trapezoidal integration over the entire OGTT for glucose tolerance assessment.

Lunch will be provided.

At 30-minutes following lunch:

Peak Exercise Testing ($VO_{2\text{peak}}$)

Participants will perform a graded exercise test on a recumbent cycle ergometer located on the WUSM CTRU. Continuous ECG/BP and oxygen consumption (VO_2) will be recorded during the graded exercise test to determine peak exercise capacity ($VO_{2\text{peak}}$). The graded exercise test protocol consists of 1-min incremental stages, beginning with a 20-watt workload, progressing every minute by 10-20-watts until volitional exhaustion or symptom limitation. Exercise tests will be considered maximal if peak heart rate $\geq 85\%$ predicted maximum (220-age) and/or respiratory exchange ratio ≥ 1.1 according to the American College of Sports Medicine⁵⁷. Peak exercise testing will be supervised by a licensed physical therapist and the CTRU nursing staff.

Ten-Repetition Maximum Strength testing (10RM)

10RM will be determined on 4-upper body and 4-lower body exercises on Universal exercise machines (Body Master®) located on the WUSM CTRU. 10-RM is the maximum amount of weight a participant can lift 10 times using proper form and only primary muscle groups required for the lifting motion. 10RM will be determined on each exercise device by trial and error.

D3 Visit 2

The evening before the study visit #2, participants will consume a standardized meal consisting of 55% carbohydrate, 30% fat, and 15% protein provided by the WUSM Bio-Nutrition Facility. The following morning, fasted participants (10 hrs) will be admitted to the WUSM CTRU at 7:00 am. Maternal weight (calibrated scale) and height (stadiometer) will be measured.

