Acute Aerobic Exercise or Resistance Exercise Session

Visit # 2 will consist of either: A) a 45-minute aerobic exercise (AE) session on a recumbent cycle ergometer at 70% $VO_{2\text{peak}}$, or B): a 45-minute resistance exercise (RE) session. The RE session will consist of 3 sets of 8-10 repetitions at their 10RM load according to the Adult NIH Molecular Transducers of Physical Activity in Humans (MoTrPAC) Study Protocol: <https://www.motrpac.org/protocols.cfm>. The acute RE session will be individualized, based on the measurements taken from a 10RM (measured without Valsalva maneuver) tests during Visit #1 for 1) knee extension, 2) knee flexion, 3) leg press (i.e. hip and knee extension), 4) ankle plantar flexion, 5) chest press, 6) seated row, 7) bicep curl (elbow flexion), and 8) overhead press. For each exercise, 3 sets of 8-10 repetitions will be performed with a 2-minute rest in between

sets. A 3-second contraction duration for the concentric and a 3-second contraction duration for the eccentric phase of the lift will be targeted. Fasting blood samples will be taken at pre-AE/RE/rest, at 20-min during AE/RE, immediately post-AE/RE/rest, and 60-min post AE/RE/rest as per MoTrPAC protocol. All visits will be separated by 1 week and rest, AE and RE visit order will be randomized through a computerized randomization program. The study scheme is presented in the Figure.

Assessment of Glucose Metabolism

At 60-min following the completion of AE/RE, a 2-hr oral OGTT will be conducted as described in Visit 1.

Assessment of Vascular Function

Endothelial and large artery function testing will be performed as described in Visit 1.

D3 Visit 3

The evening before the study visit #3, participants will consume a standardized meal consisting of 55% carbohydrate, 30% fat, and 15% protein provided by the WUSM Bio-Nutrition Facility. The following morning, fasted participants (10 hrs) will be admitted to the WUSM CTRU at 7:00 am. Maternal weight (calibrated scale) and height (stadiometer) will be measured.

Acute Aerobic Exercise or Resistance Exercise Session

Visit # 3 will consist of either: A) a 40-minute aerobic exercise (AE) session on a recumbent cycle ergometer at 70% VO_{2peak} , or B): a 40-minute resistance exercise (RE) session as described above.

Assessment of Glucose Metabolism

At 60-min following the completion of AE/RE, a 2-hr oral OGTT will be conducted as described in Visit 1.

Assessment of Vascular Function

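### As the visits are written, rest days admit at 8:00 am and exercise days at 7:00 am, so the OGTT clock time follows the rest-versus-exercise contrast

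*Combined protocol and SAP*

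**What the plan says.** - **Admission.** D2 brings participants for Visit 1 to the research unit of "Washington University School of Medicine (WUSM CTRU) at 8:00 am". The only session in that visit is 45 minutes lying in bed. At Visit 2 the participant "will be admitted to the WUSM CTRU at 7:00 am", and Visit 3 gives the same hour. Visits 2 and 3 offer only AE or RE.
- **Fast and meal.** In D2, "fasted participants (10 hrs) will be admitted to the Clinical Translational Research Unit", after a standardised meal the evening before. D3 repeats the meal and the 10-h fast. No meal hour is given.
- **Sessions.** Rest lasts 45 min, a Visit 2 session 45 min and a Visit 3 session 40 min.
- **OGTT.** For rest, "At 60-min following the end of the rest period, a 2-hr oral OGTT will be conducted". D3 uses the same 60-min interval after AE or RE.
- **Order.** D3 says the order of rest, AE and RE is randomised by computer. It also individualises the RE session, "based on the measurements taken from a 10RM (measured without Valsalva maneuver) tests during Visit #1", and sets AE at 70% of VO2peak, which is likewise measured late in Visit 1.
- **Analysis.** F2 compares the three conditions by repeated measures ANOVA with post-hoc tests. It expects to detect differences between exercise and rest, and names the Matsuda insulin sensitivity index (ISI) as one of two primary outcomes.

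**The concern.** The plan standardises the evening meal, the fast and the interval from session to OGTT, but not the hour at which the day starts. Exercise cannot be dosed until the Visit 1 tests are done, so as written every rest day starts at 8:00 am and every exercise day at 7:00 am. Scheduled admission hour is then the same variable as rest versus exercise. The within-woman comparison does not average that difference out, and F2 has no term for it.

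ISI comes from one post-session OGTT per visit, with no pre-session ISI to subtract. What is at stake is an avoidable difference in clock time, and in either last-meal hour or fasting time, along the main contrast of a pilot meant to inform a larger trial.

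**Working it through.** The plan states no OGTT clock time, so there is no figure of its own to reproduce.

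**Formula.** OGTT start = admission + preparation + session + 60 min. Let P be preparation before rest, P + d preparation before exercise, and S the exercise session length. Then:

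gap (rest minus exercise) = (8:00 + P + 45 + 60) − (7:00 + P + d + S + 60) = 105 − S − d min.

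**Stated session lengths, equal preparation (d = 0, assumed).**
- Rest: 9:45 am + P.
- S = 45: exercise at 8:45 am + P; gap 105 − 45 = 60 min.
- S = 40: exercise at 8:40 am + P; gap 105 − 40 = 65 min.

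**What could narrow the gap.**
- *A longer RE session.* D3 prescribes 8 exercises × 3 sets = 24 sets of 8–10 repetitions at 3 + 3 = 6 s each. Lifting time is 24 × 8 × 6 s = 19.2 min to 24 × 10 × 6 s = 24.0 min. The 2-min rests add 16 × 2 = 32 min if taken only within exercises, 23 × 2 = 46 min between all sets, or 24 × 2 = 48 min after every set. RE then takes 51.2–56.0, 65.2–70.0 or 67.2–72.0 min, against the stated 45 or 40. With d = 0 the gaps are 53.8–49.0, 39.8–35.0 and 37.8–33.0 min.
- *A vascular test before exercise only.* D2 says the finger tonometry test "will be measured before, and immediately post-exercise to assess digital pulse volume responses", but its Visit 1 sequence lists the test only after rest. The test takes 10 + 3 + 5 = 18 min: "Following 10 min of baseline signal recording, a blood pressure cuff is inflated for 3-min", and 5 min are recorded after release. With d = 18 the gap is 42 min (S = 45) or 47 min (S = 40); for RE at its prescribed content it is 35.8–31.0, 21.8–17.0 or 19.8–15.0 min.
- *Other preparation.* Large-artery testing before exercise and equipment set-up have no stated duration.

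**What could widen it.** D2 lists a step that D3 does not: "Whole-body fat will be quantified using through skin-fold anthropometry". No duration is given. If it took 5–15 min (assumed), the 65-min gap would become 70–80 min.

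**Fast.** Ten hours before 8:00 am is 10:00 pm; ten hours before 7:00 am is 9:00 pm. The last-meal hour differs by one hour.

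**Equal admission only.** With Visit 1 moved to 7:00 am, the gap is 45 − S − d. With d = 0 it is 0 (S = 45), +5 (S = 40), or −6.2 to −25.0 for RE of 51.2–70.0 min. With d = 18 it is −18, −13, or −24.2 to −43.0. A negative value means the exercise OGTT starts later.

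**The case against.** - **Randomised order.** If all six orders were used equally and times followed visit number, the admission gap for rest versus either exercise would be +60 in two orders, −60 in two and 0 in two, mean 0. That is correct arithmetic, but orders that put exercise first cannot be run as written, because the loads come from Visit 1. The point therefore depends on the rest-first reading and is partly a sub-item of it.
- **Existing controls.** If the 10-h fast is kept strictly, fasting time at the OGTT is 10 h + P + 45 + 60 = 11 h 45 min + P on the rest day, and 11 h 45 or 11 h 40 min + P on exercise days with equal preparation. So fasting time is nearly matched, and clock time and last-meal hour are what differ. A longer fast before rest arises only if the meal hour is held fixed, which departs from the stated 10 h. Pre-session glucose and insulin allow a check of fasting state, though they cannot give ISI. This objection stands, and it limits the point.
- **Missing schematic.** The figure of the rest, AE and RE sessions was not available and may give timings. Only the text can be said to give no reason.
- **Pilot purpose and no shown effect.** This is a 15-woman proof-of-concept study, and nothing in the documents links an hour's shift to ISI. This stands too, and it is why the point is minor.
- **Weight of the remedy.** Staggered starts need a planned RE length, and the prescription and the stated length disagree. An overrun would break either the clock target or the 60-min interval, so the plan must say which gives way.

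**Conclusion.** The point holds as a minor, avoidable procedural difference. At the stated session lengths and with equal preparation, the rest OGTT would start 60–65 min after the exercise OGTT would; under a 10-h fast at admission, the last-meal hour differs by one hour. This rests on the visits being run as written, rest first, and on the text alone.

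Two stronger readings are not supported:
- A reader might take 17–65 min, from 70-min RE with pre-exercise tonometry up to a 40-min session with equal preparation, as the bounds of the gap. They are not bounds. Rests after every set give 15 min, unlisted exercise-day preparation could lower the gap further, and Visit 1 skin-folds could push it past 65. The RE figures also override the stated session lengths.
- A reader might infer that the exercise effect on ISI is biased in a known direction, or that an error rate is affected. The documents give neither size nor direction.

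The fixed rest-first order is the larger issue, and the change below does not cure it.

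**What to change.** In D2 and D3:

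1. Set one target OGTT clock time for all three visits.
2. Count the session start back from it: target − 60 min − planned session length. For a 9:45 am OGTT the start is 8:45 am − S: 8:00 am for 45 min, 8:05 am for 40 min, and about 7:54 to 7:35 am for RE of 51–70 min.
3. If a session overruns, keep the 60-min interval and let the clock time slip.
4. Use one admission time, early enough for the longest preparation. With 7:00 am, the starts above leave 35–65 min. At the 35-min end, an 18-min tonometry test leaves 17 min for weight, height, blood sampling and any large-artery testing. If that is too tight, admit earlier or move the target later.
5. Record actual session and OGTT start times on the case report form.

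One admission time without the OGTT target is not enough, since exercise OGTTs could still start up to 43 min later than rest under the RE lengths of 51–70 min, and more if preparation or RE runs longer.

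The cost is an earlier start on the rest day if 7:00 am is used, staggered session starts for staff, and a few form fields. There are no extra visits or procedures, and the 60-min interval is unchanged. The hour itself is the sponsor's choice. If the present difference is deliberate, the protocol should give the reason.

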The primary outcome variables for this pilot trial are the Matsuda Whole-Body Composite Insulin Sensitivity Index (ISI) following an oral glucose tolerance test (OGTT), and the digital pulse volume response to arterial occlusion (blood pressure cuff) measured by reactive hyperemia peripheral tonometry (EndoPAT 2000, Itamar Medical, Caesarea, Israel). $ISI = 10\,000 / \sqrt{(\text{glucose}_{\text{fasting}} \times \text{insulin}_{\text{fasting}}) (\text{glucose}_{\text{mean}} \times \text{insulin}_{\text{mean}})}$ is strongly associated with the glucose-clamp procedure which is considered the gold standard for measuring insulin sensitivity^{50,51}. The EndoPAT 2000 has good reproducibility (ICC=0.74) and has been validated as a measure of endothelial function

with an 82% sensitivity and 77% specificity to diagnose coronary endothelial dysfunction⁵².

C4 Confirmation of Patient Eligibility

Confirm patient eligibility by collecting the information listed below:

1. Registering MD's name
2. Patient's race, BMI and DOB
3. Three letters (or two letters and a dash) for the patient's initials
4. Copy of signed consent form
5. Completed eligibility checklist, signed and dated by a member of the study team
6. Copy of appropriate source documentation confirming patient eligibility

C5 Assignment of UPN

Each patient will be identified with a unique patient number (UPN) for this study. All data will be recorded with this identification number on the appropriate CRFs.

Study Design

C6 Overview or Design Summary

The overall study design is a quasi-randomized, observational, 3-condition comparison of the acute effects of rest, resistance exercise or aerobic exercise on glucose metabolism and vascular function in obese women (n=15) during mid pregnancy.

C7 Subject Selection and Withdrawal

7.a Inclusion Criteria

1. First trimester BMI ≥ 30.0 and <45.0 kg/m² (calculated from clinical weight and height)
2. Singleton gestation, between 23 weeks and 0/7 days and 28 weeks and 0/7 days
3. Normal fetal anatomy (no major structural abnormalities identified on standard of care survey before enrollment)
4. Established prenatal care at Women's Health Clinic before 18 weeks of gestation, plans to deliver at Barnes-Jewish Hospital
5. Permission from Obstetrics physician provider to participate in study.

7.b Exclusion Criteria

1. Gestational or pre-gestational diabetes diagnosis
2. Inability to provide voluntary consent

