The primary objective of this pilot grant is to obtain preliminary data necessary for proof-of-concept and for sample size estimation for a large, multisite clinical trial. However, we anticipate having enough power to demonstrate independent acute effects of AE and RE on glucose metabolism and vascular function necessary for potential publication of these pilot data. Using data from non-gravid adults with obesity, Newsom et al.⁵⁸ demonstrated an increase in next day insulin sensitivity following a low-intensity AE session. Rynders et al.⁵⁹ found lower 2-hr OGTT glucose value following acute AE in prediabetic non-gravid adults. Further, Breen et al.⁶⁰ demonstrated a 17% improvement in glucose AUC following acute RE in normoglycemic non-gravid adults. Using these data, a sample size of n=14 would be adequate to see a statistical difference with either acute AE or RE on glucose metabolism. For vascular function, Haynes et al.⁶¹ demonstrated increased (~4-12%) reactive hyperemic responses following acute RE and AE in older men. Also, Kingsley and Figueroa⁶² found increased reactive hyperemic responses following acute RE in 24 obese older women. These data suggest that a sample size of n=11 will be necessary to see statistically significant differences in vascular function pre/post acute AE or RE, assuming similar responses.

F2 Statistical Methods

We plan to assess differences in glucose metabolism and vascular function between the three different conditions (i.e. acute, AE, RE) using a repeated measures ANOVA with post-hoc testing. We anticipate detecting differences between AE/RE and rest but likely will not have the power to detect potential differences between AE and RE. The two primary outcomes will be the Matsuda ISI and endothelial hyperemic response (digital pulse volume). Other glucose metabolism and plasma analyte variables will be secondary outcomes.

G Study Monitoring, Auditing, and Inspecting

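### Glucose and insulin are drawn before every rest and exercise session, but the comparison of post-session Matsuda ISI does not use them as a same-visit baseline

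*Combined protocol and SAP*

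**What the plan says.** - **Pre-session samples.** D3 (Visit 2): "Fasting blood samples will be taken at pre-AE/RE/rest, at 20-min during AE/RE, immediately post-AE/RE/rest, and 60-min post AE/RE/rest". D2 lists plasma glucose and insulin in the draw before the 45-minute rest. The *Plasma Hormone and Metabolites* paragraph confirms collection before rest, aerobic exercise (AE) and resistance exercise (RE).
- **When ISI is measured.** D2, rest: "At 60-min following the end of the rest period, a 2-hr oral OGTT will be conducted". D3, exercise visits: "At 60-min following the completion of AE/RE, a 2-hr oral OGTT will be conducted as described in Visit 1". No OGTT is done before a session, so ISI exists only afterwards.
- **OGTT draws.** D2: "Venous samples for glucose, insulin, and C-peptide will be drawn at time 0 and then 30, 60, 90 and 120 minutes after starting" the glucose drink.
- **Primary outcomes.** F2: "The two primary outcomes will be the Matsuda ISI and endothelial hyperemic response (digital pulse volume").
- **Analysis.** F2 plans a repeated measures ANOVA over the three conditions, followed by post-hoc tests. It names no baseline, change score or covariate. Other glucose measures and plasma analytes are secondary outcomes.
- **Order.** D3 (Visit 2) says that a computer program randomises the order of rest, AE and RE. The visit descriptions, however, put rest at Visit 1 and the two exercise sessions at Visits 2 and 3.

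**The concern.** The three ISI values for one woman come from three days. D2 allows the visits anywhere in gestation weeks 23 to 30, at least 4 days apart; D3 says one week apart. A woman's basal glucose and insulin can differ between those days for reasons unrelated to the session. In the planned analysis all of that variation goes into the residual against which exercise is compared with rest.

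Part of it is already measured. The pre-session draw comes before that visit's session, so the session cannot affect it, and it reflects the woman's basal state that morning. With 15 women, and a pilot meant to supply variance estimates for a larger trial, leaving this information out of the primary comparison is a real if modest loss.

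**Working it through.** **1. The plan's own figure.** F1 calls n=14 adequate for glucose metabolism. This cannot be reproduced: F1 gives no alpha, power or SD, and no effect on the ISI scale. The present point does not alter that figure. For scale, a paired t-test at an assumed two-sided alpha of 0.05 and 80% power detects a standardised paired difference of 0.81 with 14 women and 0.78 with the planned 15.

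**2. Error degrees of freedom.** For 15 women and 3 conditions: (15 − 1) × (3 − 1) = 28. Visit effects, if separable from condition, take 2 (28 − 2 = 26). The covariate takes 1 more.

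**3. What the covariate is.** HOMA-IR = insulin × glucose / 22.5, so log HOMA-IR = log(glucose × insulin) − log 22.5, apart from units. The constant does not affect the slope, so either form gives the same adjustment.

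**4. Gain.** Residual variance after adjustment ≈ σ²(1 − ρ²), where ρ is the within-woman correlation of pre-session log HOMA-IR with log ISI. Equivalent number of women = 15/(1 − ρ²). Detectable difference, in unadjusted paired SDs = 0.778 × √(1 − ρ²). The last two ignore the lost degree of freedom. All values of ρ are assumed.

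| ρ | Variance reduction | 1 − ρ² | 15 women act like | Detectable difference |
|---|---|---|---|---|
| 0.2 | 4% | 0.96 | 15.6 | 0.76 |
| 0.3 | 9% | 0.91 | 16.5 | 0.74 |
| 0.5 | 25% | 0.75 | 20.0 | 0.67 |
| 0.7 | 49% | 0.51 | 29.4 | 0.56 |

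**5. Break-even.** Spending one of 28 degrees of freedom costs about 1/28 = 3.6%. This is recovered when ρ² = 1/28, that is ρ = 0.19. With visit in the model, ρ² = 1/26 gives ρ = 0.20.

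**6. Side check on the ISI fasting term.** Let q be the glucose × insulin product at OGTT time 0 divided by its pre-session value. With the OGTT means held fixed, ISI using time 0 divided by ISI using the pre-session draw is 1/√q. Assumed q = 0.8 gives 1.118 (+11.8%), q = 0.7 gives 1.195 (+19.5%), and q = 1.25 gives 0.894 (−10.6%).

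**The case against.** The best case for the plan is that a within-woman comparison of post-session ISI needs no baseline when order is randomised. Day-to-day variation is then noise and not bias. One pre-session draw cannot give a baseline Matsuda ISI, which would need an OGTT before the session. The gain rests wholly on an assumed correlation and could be as small as 4%. A covariate that changes at each visit does not fit a standard repeated measures ANOVA. The pre-session values are also not discarded, since F2 covers plasma analytes as secondary outcomes. All of this stands. It limits the point to precision and does not remove the gain.

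A reader might infer two stronger things that the documents do not support.

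*That the missing baseline biases the exercise effect.* Under the randomised order stated in D3 it does not. If rest is always Visit 1, condition is confounded with time, but that comes from conflicting text on visit order, and a covariate does not cure it.

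*That the ISI fasting term would be taken from before exercise,* because D3 calls every session sample fasting and the formula attaches no time point. Step 6 shows that the choice would change the index in either direction. But C3 names the outcome as the "Matsuda Whole-Body Composite Insulin Sensitivity Index (ISI) following an oral glucose tolerance test (OGTT"). The formula stands in the OGTT paragraph, where the only draw before glucose is time 0, and HOMA-IR in the same sentence is indexed to t0. The label is accurate, because no intake is described before the drink, and it also covers the 60-minute sample, which is when the OGTT starts. Time 0 is the natural reading. The cited index methods and the study schematic, which might settle it, could not be consulted.

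**Conclusion.** The point holds as a missed gain in precision on one of the two primary outcomes. A same-visit baseline for basal insulin resistance is collected in all three conditions and has no role in the planned comparison of ISI. The gain is about ρ² of the residual variance: 4% at ρ = 0.2 and 49% at ρ = 0.7, against a cost of about 3.6%. It is worth having unless ρ is below about 0.2. The size depends on ρ, which the documents do not give, and on an approximately linear relation on the log scale. The planned comparison is not invalid without the covariate. The unspecified time point of the ISI fasting term is a small gap in wording and not an error.

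**What to change.** 1. In F2, analyse log ISI in a linear mixed model with condition and visit as fixed effects, woman as a random effect, and same-visit pre-session log(glucose × insulin), that is log HOMA-IR, as a covariate. Describe it as a baseline for basal insulin resistance, not as a baseline ISI.
2. Tabulate the pre-session value by visit, so that gestational drift or carry-over from an earlier session can be seen.
3. Reconcile separately the statement that rest, AE and RE are randomised in order with the visit descriptions that put rest first. If rest is always Visit 1, the Visit 1 effect and the rest effect are the same column of the model and cannot be separated.
4. As a minor clarification, add one line saying that the ISI fasting terms are the OGTT time-0 glucose and insulin in all three conditions.

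Cost: no new samples or visits, one of about 28 error degrees of freedom for the covariate (up to two more for visit), and a mixed model in place of a standard repeated measures ANOVA. That is a change of method, though a small one, and should be written into F2 before the data are analysed.
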